8.1.2 Analysis of secondary endpoints

Analysis will be descriptive.

Categorical variables will be presented as the number and proportion of patients with the endpoint in the treated population. For the survival endpoint numbers and proportions will be presented for both treated and control patients.

Continuous variables will be presented as the median and range for the intervention patients.

8.1.3 Analysis of subgroups

Not applicable

8.1.4 Covariate adjusted analysis

Not applicable

8.1.5 Matching of controls to patients

Potential controls will be screened for inclusion and exclusion criteria including a cardiac aetiology. Only patients cared for concurrently with the study will be used. Controls will be individually matched to up to 5 patients, using age (within 5 years) and time of LAS attendance on scene (within 5 minutes). Matching with replacement will be performed but also matching without replacement in a planned sensitivity analysis.

8.2 Assumptions for analysis.

The analysis is descriptive and makes no assumptions about the data.

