#### **4.3 Current UK clinical practice for OHCA**

Most ambulance services in England follow the European Resuscitation Council guidelines for pre-hospital resuscitation [18], which advise at least 20 minutes of CPR for all attempted resuscitations. If there is failure to achieve ROSC and the cardiac rhythm is asystole, then the resuscitation is terminated, typically. Resuscitation may also be stopped if the cardiac rhythm is pulseless electrical activity (PEA) after discussion with a clinical support desk. If the rhythm is refractory ventricular fibrillation/tachycardia (VF/VT), the patient will be transported with on-going CPR to the nearest emergency department or heart attack centre.

Hospital based ECPR is provided in a few EDs and heart attack centres throughout England on an ad-hoc, case-by-case basis. The UK Resuscitation Council 2015 guidelines recommend that ECPR should be considered as a rescue therapy for select patients in whom initial ALS techniques are unsuccessful [19]. There is no national protocol for its use and it has never been performed in a pre-hospital setting in the UK.

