3.1 Design

The study is a single centre feasibility study of a complex intervention. The study aims to recruit six intervention patients. The study will only be performed between 8.00 am and 5.00pm on study days when the ECMO team is available. It is anticipated that this will be 2-3 days per week. Patients will be matched to other patients managed by LAS on non-study days, based on their suitability for ECPR in order to compare mortality between study and non-study days.

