5.2 Exposure to study drug

Not applicable.

6 Demographics and Baseline characteristics

Age, gender, ethnicity and time of LAS attendance on scene will be described for intervention patients and matched controls. In addition, we will describe the following risk factors – diabetes, PVD, IHD, CVA, smoking, frailty index.

7 Interim analysis and timing for analysis.

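### Cardiac rhythm is not matched on, adjusted for or described in the survival comparison, the only one made with controls, so a rhythm imbalance would be neither removed nor seen

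*SAP*

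**What the plan says.** SAP 3.1 sets the aim of the matching: patients are matched to others managed on non-study days "based on their suitability for ECPR in order to compare mortality between study and non-study days". SAP 8.1.5 gives the rule. Potential controls are screened against the eligibility criteria, including cardiac aetiology, and are then "individually matched to up to 5 patients, using age (within 5 years) and time of LAS attendance on scene (within 5 minutes"). Protocol 10.2 lists age, time of first LAS attendance and presumed cardiac aetiology, and applies individual, propensity score and GenMatch matching.

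SAP section 6 states the baseline description: "Age, gender, ethnicity and time of LAS attendance on scene will be described for intervention patients and matched controls". It adds the risk factors "diabetes, PVD, IHD, CVA, smoking, frailty index". The sections "8.1.3 Analysis of subgroups" and "8.1.4 Covariate adjusted analysis" are both marked not applicable. SAP Table 3 and SAP 8.1.2 make survival the only endpoint reported for controls.

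On usual care when ROSC has not been achieved, protocol 4.3 separates the rhythms. For VF/VT: "If the rhythm is refractory ventricular fibrillation/tachycardia (VF/VT), the patient will be transported with on-going CPR". For PEA: "Resuscitation may also be stopped if the cardiac rhythm is pulseless electrical activity (PEA) after discussion with a clinical support desk". For asystole, resuscitation typically ends.

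**The concern.** Suitability for ECPR is the stated basis of the matching, but after screening only age and attendance time separate one potential control from another. Rhythm bears on a control's survival in two ways. It is strongly prognostic in the LAS figures that the protocol cites, and it governs whether resuscitation continues under usual care. If the six treated patients and their controls have different rhythm mixes, part of any survival difference reflects that mix, and no planned table would show it.

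Protocol 4.5 and SAP 2.2 say the data should help to estimate the size of outcome benefit for a later trial. A reader using the contrast for that purpose would need the rhythm mix.

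**Working it through.** **1. Where rhythm could enter, and whether it does.**
- Eligibility (protocol 6.1, 6.2): there is no initial-rhythm criterion. The exclusion needs absent signs of life together with absent electrical activity at the time-out or low end-tidal carbon dioxide. VF/VT and PEA both remain eligible.
- Matching factors (SAP 8.1.5, protocol 10.2): no. Cardiac aetiology is already an inclusion criterion, so it separates nobody after screening. The propensity score and GenMatch methods cannot balance a factor that they are not given.
- Adjustment and subgroups (SAP 8.1.3, 8.1.4): none.
- Baseline description (SAP section 6): not listed.

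**2. The plan's own figures (protocol 4.1).**
- Shockable, bystander-witnessed: 371/542 = 68.5% mortality, so survival is 171/542 = 31.5%.
- Non-shockable: 3,353/3,440 = 97.5% mortality, so survival is 87/3,440 = 2.5%.
- Difference: 29.0 points.

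Both stated percentages reproduce. Two limits apply. These are not arrests still refractory at 20 minutes. The witnessed label on the 3,440 also needs checking. Of 4,389 attempts at 91% mortality, about 3,994 died. Removing 371 + 3,353 = 3,724 leaves 270 deaths among the other 4,389 − 542 − 3,440 = 407 patients, a survival of 34% (28% to 39% allowing for rounding of the 91%). That exceeds the shockable group's survival, so the 3,440 may include unwitnessed arrests, and the 29.0 points may not be due to rhythm alone. The figures show that rhythm is prognostic. They do not measure the bias here.

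**3. Shift from a rhythm gap, with no ECPR effect.**
Shift = (shockable share in treated − shockable share in controls) × (survival if shockable − survival if non-shockable).

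For an assumed 25-point gap:
- assumed refractory survival 5% v 2.5%: 0.25 × 2.5 = 0.6 points
- assumed refractory survival 10% v 1%: 0.25 × 9 = 2.3 points
- protocol 4.1 rates: 0.25 × 29.0 = 7.3 points

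**4. How large a gap chance alone produces.**
With k of 6 treated patients shockable, k ~ Binomial(6, p), the mean absolute gap from the source mix is E|k/6 − p|. It is 15.6 points at p = 0.5 and 14.8 points at p = 0.25 or 0.75 (the values of p are assumptions). Multiplying by the three survival differences gives mean shifts of 0.37 to 0.39, 1.33 to 1.41 and 4.30 to 4.53 points. A gap above 25 points has probability 21.9% at p = 0.5 and 3.8% at p = 0.25 or 0.75.

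**5. Sampling error for comparison.**
One survivor in six is 1/6 = 16.7 points. With 2 of 6 surviving, the exact (Clopper-Pearson) 95% interval is 4.3% to 77.7%.

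**The case against.** The strongest case against has five parts.

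- **No selection on rhythm is shown.** Study days depend on ECMO team availability (protocol 7.3, SAP 3.1), and controls are concurrent and screened on the same criteria. What is demonstrated is chance imbalance, which is part of sampling error. This stands. A reader might infer that the comparison favours ECPR because resuscitation of PEA controls may be stopped. The documents do not support that: nothing in them makes the treated group more shockable than its controls, and an imbalance could run either way.
- **The large shifts use unsuitable rates.** This stands. A reader might take the 29.0-point gap, or the 7.3-point shift, as the size of the bias. Neither is, because no survival by rhythm is given for refractory arrests.
- **Protocol 4.3 concerns rhythm when ROSC has failed, which can differ from initial rhythm.** This stands. Matching on initial rhythm addresses prognosis and would not fully equalise usual care, so rhythm at about 20 minutes should also be described if it is held.
- **No stated decision turns on the contrast.** This is largely right. A larger trial is conditional on feasibility within 30 minutes, SAP 3.7 rules out hypothesis tests, and six patients cannot estimate a benefit well with or without rhythm. It limits the importance of the point. It does not explain why diabetes and smoking are described and rhythm is not.
- **Matching on rhythm may thin the controls and leave partly matched sets undefined.** This is fair, and is why the fix needs an explicit rule.

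**Conclusion.** The omission is confirmed in both documents: rhythm is absent from the matching, the adjustment and the description in the one controlled comparison. The consequence is a survival benchmark whose rhythm mix cannot be seen. No systematic bias is established, and no direction.

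The size of any shift is unknown. Under the assumed rates and mixes above, chance imbalance moves the contrast by about 0.4 to 4.5 points on average, less than the 16.7 points that one survivor represents. The primary endpoint concerns timing and is unaffected. This is a worthwhile, low-cost improvement to a descriptive comparison and no threat to the main result.

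**What to change.** 1. **SAP section 6:** for treated patients and matched controls, describe initial rhythm (shockable / non-shockable), and rhythm at about 20 minutes if the LAS database holds it.
2. **SAP 8.1.2:** list survival by rhythm in both groups, descriptively.
3. **SAP 8.1.5 and protocol 10.2:** add initial rhythm as a matching factor. Suggested rule for individual matching: *where at least one control of the same initial rhythm lies within the age and time limits, use only such controls, up to 5; where none exists, or rhythm is missing, keep the age- and time-matched controls and flag the patient as not rhythm-matched.* Include rhythm as a covariate in the propensity score and GenMatch matching.
4. **Before the single LAS data transfer (protocol 10.2, 13.3):** request the rhythm fields. The rhythm-specific figures in protocol 4.1 suggest that LAS records rhythm, but neither section confirms that it will be supplied.

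The cost is wording in three SAP sections and one protocol section, plus one or two data fields. Some patients will have fewer than 5 controls, and the survival-by-rhythm cells will be very small. Under this rule, no patient loses all controls because of rhythm.

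Two nearby matters should be reconciled separately and do not bear on this point. SAP 8.1.5 words the ratio as controls matched to up to 5 patients, whereas protocol 10.2 matches each patient to many. The SAP also gives one matching technique and the protocol three, possibly because the SAP was written from protocol version 2.0 of October 2018.

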8.3 Methods for handling of missing data and outliers

All available data will be used for each endpoint. Due to the small number of patients and the descriptive nature of the analysis, data will not be imputed.

8.4 Multiple comparisons

Not applicable

8.5 Multiple-centre studies

Not applicable

9 Safety analysis

The number of subjects having at least one AE will be presented. The number of subjects with AEs of mild/moderate/severe intensity will be shown as well as the total number of AEs allowing multiple events per patient.

SAEs will be listed along with details including whether the event is unexpected and whether it is thought to be related to the treatment.

10 References

1. Virdi, G., S. Picton, and R. Fothergill *London Ambulance Service NHS Trust Cardiac Arrest Annual Report: 2014/15*. 2015.
2. Fagnoul, D., A. Combes, and D. De Backer, *Extracorporeal cardiopulmonary resuscitation*. Curr Opin Crit Care, 2014. 20(3): p. 259-65.
3. Soar, J., et al., *Adult advanced life support guidelines*. 2015.
4. Keith, R.A., et al., *The functional independence measure: a new tool for rehabilitation*. Adv Clin Rehabil, 1987. 1: p. 6-18.

11 Document history and version control

All versions will be dated and numbered in the format N.x, where N is a numeric value that is increased when a major change is made. The postscript x relates to minor changes typically for typographical errors that do not substantially alter the conduct of the tool.

The full history is outlined in Table 4.

Table 4 Version history

Version	Date	Notes
1.0	10 April 2019	First authorised version of Statistical Analysis Plan
